- On-study laboratory assessments should be drawn within 72 hours prior to dosing.
- Adverse event assessments should be documented at each clinic visit.
- 
- Study drug is administered as an IV infusion over 60 minutes on Treatment Day 1 of each cycle until disease progression or discontinuation due to toxicity, withdrawal of study consent, or the study ends. Treatment beyond progression is allowed in certain instances as described in [Section 4.3.8](#).
- Study drug dosing may be delayed for toxicity. See [Sections 4.3.2](#) and [4.3.4](#).
- Subjects will be evaluated for tumor response according to the 2007 revised International Working Group Criteria for Malignant Lymphoma ([Appendix 2](#)) by spiral CT/MRI beginning at week 9 and continuing every 8 weeks (\pm 1 week) through the first 8 months, every 12 weeks (\pm 2 weeks) months 9-24, and then every 6 months (\pm 3 weeks) thereafter until disease progression is documented or until the subject initiates a preparative regimen for allogeneic SCT or ASCT, whichever occurs earlier. If the subject discontinues treatment prior to disease progression, tumor assessment will continue in the follow-up phase.
- Screening/Baseline and all subsequent scans will be submitted to an IRRC, once the subject has been enrolled and throughout the study period.
- Quality of Life (QoL) tools must be completed at Treatment Day 1 prior to the first dose of study drug. Following that, QoL tools will be completed according to the schedule in [Table 5.1-2](#).
- This phase ends when the subject is discontinued from study therapy. For a complete list of reasons for treatment discontinuation, see [Section 3.5](#) and [4.3.5](#).

Follow-Up Phase (See [Table 5.1-3](#)):

- Begins when the decision to discontinue a subject from study therapy is made (no further treatment with study therapy).

- Subjects will have two follow-up visits for safety. Follow-up visit 1 (X01), 35 days from the last dose (+/- 7d) and follow-up visit 2 (X02) 80 days (+/- 7d) later. After X02, subjects will be followed every 3 months for ongoing drug-related adverse events until resolved, return to baseline or deemed irreversible, or until lost to follow-up, or withdrawal of study consent.
- [REDACTED]

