5.3 Safety Assessments

At baseline, a medical history will be obtained to capture relevant underlying conditions. The baseline examinations should include weight, height, ECOG Performance Status, BP, HR, temperature, and oxygen saturation by pulse oximetry at rest and after exertion should be performed within 28 days prior to first dose. Baseline signs and symptoms are those that are assessed within 14 days prior to first dose. Concomitant medications will be collected from within 14 days prior to the first dose through the study treatment period (see [Table 5.1-1](#)).

Baseline local laboratory assessments should be done within 14 days prior to first dose to include: CBC w/differential, LFTs (ALT, AST, total bilirubin, alkaline phosphatase), uric acid, BUN or serum urea level, creatinine, Ca, Mg, Na, K, Cl, P, LDH, amylase, lipase glucose, urinalysis, TSH, and Hep B and C testing (HBV sAg, HCV Ab, or HCV RNA) (see [Table 5.1-1](#)). Pregnancy testing for WOCBP (done locally) must be performed at baseline (within 28 days prior to first dose) and repeated within 24 hours prior to the initial administration of study drug, then every 4 weeks (\pm 7 days) regardless of dosing schedule.

Subjects will be evaluated for safety if they have received any study drug. Toxicity assessments will be continuous during the treatment phase. During the safety follow-up phase (Follow-up visits X01 and X02, [Table 5.1-3](#)) toxicity assessments should be done in person. Once subjects reach the survival follow-up phase, either in-person visits or documented telephone calls/email correspondence to assess the subject's status are acceptable.

Adverse events and laboratory values will be graded according to the NCI-CTCAE version 4.0.

On-study weight, ECOG performance status, and vital signs should be assessed at each on-study visit prior to nivolumab dosing and at Cycle 1 Day 8. Vital signs should also be taken as per institutional standard of care prior to, during and after dosing. Oxygen saturation by pulse oximetry at rest and after exertion should be assessed at each on-study visit prior to nivolumab

dosing. The start and stop time of the nivolumab infusion should be documented. Physical examinations are to be performed as clinically indicated. If there are any new or worsening clinically significant changes since the last exam, report changes on the appropriate non-serious or serious adverse event page.

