6.2.1 Nonserious Adverse Event Collection and Reporting

The collection of nonserious AE information should begin at initiation of study drug. Nonserious AE information should also be collected from the start of a placebo lead-in period or other observational period intended to establish a baseline status for the subjects.

Nonserious AEs should be followed to resolution or stabilization, or reported as SAEs if they become serious (see [Section 6.1.1](#)). Follow-up is also required for nonserious AEs that cause interruption or discontinuation of study drug and for those present at the end of study treatment as appropriate. All identified nonserious AEs must be recorded and described on the nonserious AE page of the CRF (paper or electronic).

All nonserious adverse events (not only those deemed to be treatment-related) should be collected continuously during the treatment period and for a minimum of 100 days following the last dose of study treatment.

Completion of supplemental CRFs may be requested for AEs and/or laboratory abnormalities that are reported/identified during the course of the study.

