### **7.6.15 Immune-mediated Adverse Events Analysis**

IMAE analyses will include events, regardless of causality, occurring within 100 days of the last dose. These analyses are limited to subjects who received immunosuppressive medication for treatment of the event, with the exception of endocrine events (hypothyroidism/thyroiditis, hyperthyroidism, hypophysitis, diabetes mellitus, adrenal insufficiency), which will be included in the analysis regardless of treatment since these events are often managed without immunosuppression.

IMAEs, serious IMAEs, IMAEs leading to discontinuation, and IMAEs leading to dose delay or reduction will be summarized by worst CTC grade and presented by IMAE Category/PT.

Time to onset, time to resolution, time to resolution with completion of immunosuppressive medication will be defined and summarized by IMAE category in the same manner as for select AEs (see [Section 7.6.6](#)) except that, other than for the endocrine category, the longest duration of IMAEs has to be associated with the use of an immune-modulating medication. Time to Resolution for Longest Any Grade or Grade 3-5 IMAE cluster per subject will be listed.

Use of immune-modulating medications for IMAE management will be summarized by IMAE category in a similar manner as for the select AEs (see [Section 7.6.7](#)).

IMAE rechallenge will be also summarized.

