### **7.6.16 Other Events of Special Interest**

In addition to select AE and immune-mediated AE, categories of other events of special interest (OESI) have been defined (i.e. myasthenic syndrome, Guillain-Barre syndrome, demyelination, pancreatitis, uveitis, encephalitis events). Worst CTC grade of any and drug-related OESI (both safety windows) will be summarized along with the time to onset and resolution. In addition, worst CTC grade of serious OESI and OESI leading to discontinuation will be summarized (both safety

windows). Lastly, OESI occurring within 100 days of the last dose in subjects who received immunosuppressive medication for treatment of the events will be tabulated by worst CTC grade and the time to onset and resolution will be provided.

[REDACTED]

[REDACTED]

[REDACTED]

[REDACTED]

[REDACTED]

still on treatment have completed 8 weeks follow-up (after the first scheduled tumor assessment). If there are 8 or fewer responses in these 37 subjects, the study will be stopped (in both the ASCT-failed and the ASCT ineligible cohorts). Otherwise, approximately 53 additional subjects will be accrued to target a total of 90 treated subjects in the ASCT failed group. Accrual and treatment will continue during the time period that the interim analysis is being conducted. This may result in more than 37 treated subjects in the event that the study is terminated for lack of efficacy. The tolerability of the regimen will continue to be evaluated by the sponsor with the investigators to ensure that it is acceptable for continued enrollment.

The following analyses will be performed at interim analysis on the first 37 ASCT-failed cohort treated subjects.

- Pre-Treatment Subject Status Summary
- End of treatment period subject status summary
- Demographic characteristics summary
- Baseline Physical Measurements summary
- Other baseline characteristics summary
- Prior cancer therapy summary
- Cumulative dose and relative dose intensity summary
- Best overall response, per IRRC
- Time to response and duration of response, per IRRC
- Event Chart for Tumor Response, Tumor Progression, Duration of Therapy and Death
- Waterfall plot of best reduction in Target Lesion, per IRRC
- Spider plot of Tumor Burden Change, per IRRC
- Best overall response, per investigator
- Kaplan Meier plot of PFS, per IRRC
- Kaplan Meier plot of overall survival
- Status of Censored Subjects, OS Analysis
- Subsequent cancer therapy summary
- Death summary

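### Medication collection stops with study treatment, but the 100-day immune-mediated AE count needs a record of immunosuppression, so non-endocrine events first treated after discontinuation may be missed

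*Protocol*

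**What the plan says.** **Collection.** Protocol 5.3 states that "Concomitant medications will be collected from within 14 days prior to the first dose through the study treatment period". Protocol 3.1 says of the treatment phase: "This phase ends when the subject is discontinued from study therapy". The follow-up phase "Begins when the decision to discontinue a subject from study therapy is made". Adverse events run longer: under Protocol 6.2.1, nonserious AEs "should be collected continuously during the treatment period and for a minimum of 100 days following the last dose of study treatment", and Protocol 6.1.1 sets 100 days after dosing stops for serious AEs.

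**Analysis.** SAP 7.6.15 states that "IMAE analyses will include events, regardless of causality, occurring within 100 days of the last dose". It then adds a condition: "These analyses are limited to subjects who received immunosuppressive medication for treatment of the event". Endocrine events are exempt and count however they were managed. The same section derives a time to resolution that also requires the immunosuppressive course to be complete, and it summarises the use of immune-modulating drugs for IMAEs.

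SAP 7.6.16 summarises OESI several ways. Only its last tabulation is restricted by medication, to "OESI occurring within 100 days of the last dose in subjects who received immunosuppressive medication for treatment of the events".

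**The concern.** For a non-endocrine event, a medication record decides whether it enters the IMAE tables. The protocol stops requiring that record when study therapy is discontinued, while the event window can remain open for weeks afterwards. An event that starts in that interval, or that starts earlier but is first given immunosuppression then, would be recorded as an AE and could still fail the filter.

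The error can run only one way: a missing medication record removes an event from these tables and never adds one. Discontinuation itself opens the gap, and immune toxicity is one of the reasons for it. Protocol 4.3.5 lists Grade 3 drug-related pneumonitis among the grounds for stopping, and the same section anticipates prolonged steroid tapers. Treatment begun after that decision lies outside required collection, as does the tail of a taper that outlasts it.

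The select-AE tables are only a partial backstop, because SAP 7.6.6 confines most of them to the 30-day window.

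**Working it through.** The plan states no figure on this point, so there is none to reproduce. The check compares the two windows.

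**1. Does the treatment period include the 100 days?** No. Protocol 3.1 ends the treatment phase at discontinuation, and Protocol 6.2.1 names the treatment period and the 100 days after last dose as separate intervals. AE collection was carried across both; medication collection was not.

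**2. Uncovered days.** Let d be the days from last dose to the discontinuation decision. The event window is 100 days (SAP 7.6.15), so uncovered days = 100 − d.

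| Decision made | d | Uncovered days |
|---|---|---|
| On the day of last dose (assumed) | 0 | 100 − 0 = 100 |
| When the next two-weekly dose is due (assumed) | 14 | 100 − 14 = 86 |
| At the general 6-week limit on delay (Protocol 4.3) | 42 | 100 − 42 = 58 |

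Day 42 is not an upper limit for d. Protocol 4.3.5 allows interruptions beyond 6 weeks in stated circumstances, steroid tapers among them. While such a subject has not been discontinued, collection continues, so the gap falls below 58 days and closes if d reaches 100.

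**3. What fraction of events could be lost?** The documents give neither IMAE rates nor onset times, so only an assumed range can be shown. Among IMAEs first treated after the treatment period, let e be the endocrine share (exempt from the filter) and c the share of the remainder whose treatment is captured by another route. The share missed is (1 − e)(1 − c):

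| e | c = 0 | c = 0.5 | c = 1 |
|---|---|---|---|
| 0 | 100% | 50% | 0% |
| 0.3 | 70% | 35% | 0% |
| 0.6 | 40% | 20% | 0% |

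The whole range from 0% to 100% is open, and c, which the documents do not fix, drives it.

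**4. Can existing visits close the gap?** X01 is 35 ± 7 days after last dose and X02 is 80 ± 7 days after X01 (Table 5.1-3, footnote a). X02 therefore falls at 35 + 80 = day 115 nominally, at the earliest 28 + 73 = day 101, and at the latest 42 + 87 = day 129. Even the earliest X02 lies beyond day 100, so recording at that visit covers the full window.

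**The case against.** The strongest objection is that the treatment data may be collected somewhere we cannot read. The text of SAP 7.4.3 on concomitant medications is redacted, some row labels in the Protocol 5.1 tables are masked, and neither the Core Safety SAP nor the case report forms are available. Serious AEs are reported for 100 days and followed to resolution or stabilization, and supplemental forms may be requested for AEs (Protocol 6.1.1, 6.2.1). Any of these could record the immunosuppressant. This stands as a limit on confidence: the absence of a readable medication row in Table 5.1-3 is weak evidence, and no actual undercount can be claimed. It does not remove the point. Protocol 5.3 is readable and sets the end of collection, supplemental forms are optional, and no readable text requires treatment data on the AE forms. A longer rule elsewhere would conflict with 5.3 and would itself need reconciling.

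Four stronger readings are tempting, and the documents do not support them.

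- *All post-treatment IMAEs are at risk.* Endocrine events count regardless of treatment. A non-endocrine event whose immunosuppression began during treatment also passes the filter, even if the taper runs on.
- *OESI rates in general are biased downward.* In SAP 7.6.16 the summaries of any, drug-related and serious OESI, and of OESI leading to discontinuation, carry no medication condition. Only the final tabulation does.
- *About 86% of late events are lost.* That figure is a share of calendar days under one assumed decision date, not a share of events.
- *Tapers running past discontinuation have no end date.* SAP Section 8 refers missing and partial non-study medication dates to a separate imputation specification that is not available. Incomplete is the most that can be said.

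**Conclusion.** The mismatch is real, and it rests on readable text. Followed as written, Protocol 5.3 does not require the record that SAP 7.6.15 needs for a non-endocrine IMAE first treated after discontinuation, or that the last OESI tabulation in SAP 7.6.16 needs. Those counts may be too low, and the resolution time tied to completion of immunosuppression may be incomplete for tapers that outlast study therapy.

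The gap is 100, 86 or 58 days of the 100-day window for decisions at day 0, 14 or 42, and shorter after a longer approved interruption. The number of events affected cannot be estimated from the documents. Confidence is moderate, because the conclusion assumes that no unseen form or specification already captures the treatment. The matter concerns safety reporting only; the primary response-rate analysis does not depend on it. It should be corrected, since the error can only lower the IMAE counts and the remedy is simple.

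**What to change.** - **Protocol 5.3:** extend collection to 100 days after last dose, at least for immunosuppressive or immune-modulating drugs given for an AE. Follow those drugs until they are stopped or the AE resolves.
- **Table 5.1-3:** record them at X01 and X02, where Protocol 5.3 already asks for in-person toxicity assessment.
- **Subjects already past those visits:** retrieve these drugs from source for non-endocrine AEs in an IMAE or OESI category with onset within 100 days of last dose.
- **If the forms already capture this:** say so in 5.3, so that the collection rule and the SAP agree.

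The cost is protocol and form-guideline wording, extra entries at two existing visits, and some retrospective data entry. No new visits or subjects are needed, and clinical management does not change. Reported IMAE rates may rise.

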5.3.1 Imaging Assessment for the Study

Images will be submitted to an imaging corelab for central review. Sites will be trained prior to scanning the first study subject. Image acquisition guidelines and submission process will be outlined in the CA209139 Imaging Manual to be provided by the corelab.

Any incidental findings of potential clinical relevance that are not directly associated with the objectives of the protocol should be evaluated and handled by the Study Investigator as per standard medical/clinical judgment.

5.4 Efficacy Assessments

The primary efficacy assessment is objective response rate (ORR), defined as a subject achieving either a partial remission (PR) or complete remission (CR) according to the 2007 revised International Working Group Criteria for Malignant Lymphoma (Appendix 2) The primary efficacy assessment, along with the secondary endpoints of DOR, CRR, CR duration, PRR, PRR duration, and PFS will be performed by an independent radiologic review committee (IRRC). Assessment of ORR, based on investigator assessments, will be examined as a secondary endpoint. Sites are required to send all on-study disease assessments to the IRRC for review.

Once subjects discontinue study therapy by proceeding to allogeneic SCT or ASCT, they will not undergo IRRC- radiographic assessments as described in Table 5.4.1-1. Instead, they will be evaluated using the following schedule. Tumor assessment (CR or non-CR) will be assessed by the investigator according to the 2007 IWG criteria and will be required on Day 100, at 6 months, 1 year and every year thereafter from the date of stem cell infusion until the first non-CR after SCT is documented. Investigators will make telephone contacts with the subject's referring hematologist/oncologist/transplant physician to obtain CR or non-CR status and document the status if subject is being followed by another physician.

5.4.1 Radiographic Assessments

Radiographic study evaluations will take place in accordance with the flow charts in Section 5.1 and Table 5.4.1-1. Baseline assessments should be performed within 28 days prior to the first dose, utilizing spiral CT or MRI. In addition to chest, abdomen, pelvis, all known sites of disease (including CNS) should be assessed at baseline. A PET scan is required at baseline for all subjects, and to confirm a complete response (CR).

On-study assessments should include chest, abdomen, and pelvis, and all known sites of disease (including CNS) and should use the same imaging method as was used at baseline.

Subjects will be evaluated for tumor response by spiral CT/MRI beginning at week 9 and continuing every 8 weeks (+/- 1 week) through the first 8 months, every 12 weeks (+/- 2 weeks) months 9-24, and then every 6 months (+/-3 weeks) thereafter until disease progression is documented or until the subject initiates a preparative regimen for allogeneic SCT or ASCT, whichever occurs earlier.

Tumor assessments for ongoing study treatment decisions will be completed by the investigator using the 2007 revised International Working Group Criteria for Malignant Lymphoma criteria. (Appendix 2)

Table 5.4.1-1: Schedule of Spiral CT-MRI Tumor Assessments			
Time On Study	Assessment Frequency	Assessment Week (day 1 of week shown)	Assessment Window
Dose 1 to 8 Months	Every 8 weeks	9, 17, 25, 33	+/- 1 week
Month 9 to 2 Years	Every 12 weeks	45, 57, 69, 81, 93	+/- 2 weeks
> 2 Years	Every 6 months	119, 145, 171+	+/- 3 weeks

Note: Once subjects discontinue study therapy by proceeding to allogeneic SCT or ASCT, they will not undergo radiographic assessments described here, but will be followed with specific schedule (see Section 5.4)

5.4.2 Assessment of Overall Tumor Burden and Measurable Disease

To serially evaluate tumor response to therapy, it is necessary to estimate the overall tumor burden at baseline and use this as a comparator for subsequent measurements. Measurable disease is defined by the presence of at least one measurable tumor lesion. When spiral CT scans have slice thickness greater than 5 mm, the minimum size for a measurable lesion should be twice the slice thickness.

At baseline, tumor lesions/lymph nodes will be categorized as measurable or nonmeasurable as follows in Sections 5.4.2.1 and 5.4.2.2.

5.4.2.1 Measurable Lesions

Measurable lesions must be accurately measured in at least two perpendicular dimensions based on Cheson 2007 criteria⁴⁸. **In order to meet eligibility criteria, subjects must have at least one lymph node or extra-nodal node with long axis measurement > 15 mm, regardless of the short axis measurement.** Additional lymph nodes are considered to be measurable for purposes of efficacy assessments if the longest axis is 11 to 15 mm AND the short axis is > 10 mm. Lymph nodes ≤ 10 mm x ≤ 10 mm will not be considered as measurable.

If possible, nodes or masses should be from disparate regions of the body and they should include mediastinal and retroperitoneal areas of disease whenever these sites are involved.

5.4.2.2 Non-Measurable Lesions

- All other lesions, including small lymph nodes (longest diameter ≤ 10 mm) as well as truly non-measurable lesions.
- Lesions considered truly non-measurable include: leptomeningeal disease, ascites, pleural or pericardial effusion, inflammatory breast disease, lymphangitic involvement of skin or lung, abdominal masses/abdominal organomegaly identified by physical exam that is not measurable by reproducible imaging techniques.

5.4.3 Specifications by Method of Assessment

5.4.3.1 Measurement of Lesions

All measurements should be recorded in the eCRF in metric notation (mm). All baseline evaluations should be performed as close as possible to the treatment start and never more than 28 days before the beginning of treatment.

5.4.3.2 Method of Assessment

The same method of assessment and the same technique should be used to characterize each identified and reported lesion at baseline and during follow-up. Imaging based evaluation should always be done rather than clinical examination unless the lesion(s) being followed cannot be imaged but are assessable by clinical exam.

